14 SAFETY REPORTING

The Investigator will monitor each patient for clinical and laboratory evidence of adverse events on a routine basis throughout the study. Should an Investigator become aware of any study drug related SAEs following this period these must also be reported as stated below. Adverse event monitoring starts from the time the patient consents to the study until they complete the trial. All reportable AEs will be followed to a satisfactory conclusion. Any reportable drug-related AEs that are unresolved at the end of treatment visit are to be followed up by the Investigator until resolution or stabilisation. All AEs reported to the Trial Office will be processed according to internal SOPs. The Trial Office may request additional information for any AE as judged necessary.

14.1 Adverse Event Definitions

An Adverse Event or experience (AE) is any untoward medical occurrence in a study subject temporally associated with the administration of an investigational medicinal product (IMP) or a comparator product, whether or not considered related to the IMP or a comparator product. An AE can therefore be any unfavourable and unintended sign, symptom, disease (new or exacerbated) and /or significant abnormal laboratory or physiological observation temporally associated with the use of a medicinal product. For marketed medicinal products, this also includes failure to produce expected benefits (i.e. lack of efficacy), abuse or misuse.

A **Serious Adverse Event (SAE)** is any AE, regardless of dose, causality or expectedness, that:

• Results in death	
• Is life-threatening	This refers to an event in which the subject was at risk of death at the time of the event. It does not refer to an event, which hypothetically might have caused death, if it were more severe.
• Requires in-patient hospitalisation or prolongs existing inpatient hospitalisation	In general, hospitalisation signifies that the subject has been admitted (usually involving at least an overnight stay) at the hospital or emergency ward for observation and/or treatment that would not have been appropriate in the physician's office or out-patient setting. Complications that occur during hospitalisation are AEs. If a complication prolongs hospitalisation or fulfils any other serious criteria, the event is serious. When in doubt as to whether hospitalisation occurred or was necessary, the AE should be considered serious.
• Results in persistent or significant incapacity or disability	This means a substantial disruption of a person's ability to conduct normal life functions. It does not include experiences of relatively minor medical significance or accidental trauma (e.g. sprained ankle), which do not constitute a substantial disruption.
• Is a congenital anomaly or birth defect	
• Is any other medically important event	Defined as an event that may jeopardise the patient or may require intervention to prevent one of the outcomes listed above. Any new primary cancer must be reported as an SAE.

An **Adverse Drug Reaction (ADR)** is an AE which is considered to be causally related to any dose of the IMP. This means that a causal relationship between the IMP and the AE is at least a reasonable possibility, i.e., the relationship cannot be ruled out.

An **Unexpected Drug Reaction** is an adverse drug reaction, the nature or severity of which, is not consistent with applicable product information (referring to information in SPC or IB).

A **Suspected Unexpected Serious Adverse Drug Reaction (SUSAR)** is a serious adverse drug reaction, the nature or severity of which is not consistent with the applicable product information (e.g. Investigator's Brochure for an unapproved investigational product or SPC for an approved product).

14.2 Clinical laboratory abnormalities and other abnormal assessments as AEs and SAEs

Abnormal laboratory findings (e.g., clinical chemistry, haematology, urinalysis) or other abnormal assessments (e.g., ECGs, X-rays and scans) that are judged by the Investigator as clinically significant will be recorded as AEs or SAEs if they meet the definitions given above.

Clinically significant abnormal laboratory findings or other abnormal assessments that are detected during the study or are present at baseline and significantly worsen following the start of the study will be reported as AEs or SAEs. However, clinically significant abnormal laboratory findings or other abnormal assessments that are associated with the disease being studied, unless judged by the Investigator as more severe than expected for the patient's condition, or that are present or detected at the start of the study and do not worsen, will not be reported as AEs or SAEs. The

Investigator will exercise his or her medical and scientific judgment in deciding whether an abnormal laboratory finding or other abnormal assessment is clinically significant.

14.3 Determining adverse event causality

The assessment of “relatedness” must be determined by a medically qualified individual and is the responsibility of the PI at site or agreed designee. AEs that will be considered related will include any AE that is documented as possibly, probably or definitely related to protocol treatment. The assessment of relatedness is made using the following:

Classification	Relationship	Definition
drug-related	Definitely related	
 Starts within a time related to the study drug administration and No obvious alternative medical explanation.
	Probably related	
 Starts within a time related to the study drug administration and Cannot be reasonably explained by known characteristics of the patient's clinical state.
	Possibly related	
 Starts within a time related to the study drug administration and A causal relationship between the study drug and the adverse event is at least a reasonable possibility.
not drug related	Probably not related	
 The time association or the patient's clinical state is such that the study drug is not likely to have had an association with the observed effect.
	Definitely not related	
 The AE is definitely not associated with the study drug administered.

The Investigator must endeavour to obtain sufficient information to confirm the causality of the adverse event (i.e. relation to surgery, study drug, background treatment, other illness, progressive malignancy etc) and give their opinion of the causal relationship between each AE and study drug. This may require instituting supplementary investigations of significant AEs based on their clinical judgement of the likely causative factors and/or include seeking a further specialist opinion.

14.4 Reference safety information (RSI) for assessment of expectedness

- The reference safety information (RSI) for the IMP M6620 (Berzosertib) is section 7 of the IB for M6620 (Berzosertib) and lists all the expected side effects associated with the use of M6620 (Berzosertib).
- The Reference Safety Information for the IMP capecitabine is the SmPC version provided by OCTO (approved for use in this trial by the MHRA).¹
- The Reference Safety Information for the IMP cisplatin is the SmPC version provided by OCTO (approved for use in this trial by the MHRA).¹

¹It is not specified that any particular brand of Capecitabine or Cisplatin must be prescribed, however irrespective of the brand prescribed, the RSI to be referenced is provided by OCTO. N.B: This may not be the latest SmPC version available online.

A copy of the current approved version of the RSI documents for each IMP must be held in the Site File for reference. Any change or update to the RSI during the trial will be made via substantial amendment.

Please note that the list of expected side effects in the SmPCs for cisplatin and capecitabine are those listed for patients receiving standard chemoradiotherapy or chemotherapy alone. It is therefore possible that in this study population, where combination of M6620 (Berzosertib) is used with standard chemoradiotherapy or chemotherapy alone, other side effects may occur, or the patient might suffer a more severe reaction.

14.4.1 Expected adverse events associated with Radiotherapy

Fatigue, oesophagitis, odynophagia, dyspnoea, nausea, vomiting, skin erythema and desquamation. Late toxicity risks of lung fibrosis, oesophageal stricture, oesophageal perforation, cardiac toxicity and secondary malignancy.

14.5 Summary of trial safety reporting requirements

Please note all standard treatment toxicities **must be** reported because the TiTE-CRM trial design is based on an expected frequency of standard treatment toxicities plus M6620 (Berzosertib) related toxicities.

Event	DLT	SAE ¹	AE/SAE	AE/SAE
AE/SAE defined as Dose limiting toxicity (DLT) defined as per NCI CTCAE v4.03		Email reporting form within 24 hours	Report in AE CRF	Non reportable
Absolute neutrophil count (ANC) $<0.5 \times 10^9/L$ for >7 days	x	x	x	
Febrile Neutropenia (ANC $<1.0 \times 10^9/L$, fever $\geq 38.5^{\circ}C$) for >3 days	x	x	x	
Infection (documented clinically or microbiologically) with Grade 3 or 4 neutropenia (absolute neutrophil count $<1.0 \times 10^9/L$)	x	x	x	
Platelets $<25 \times 10^9/L$ (Grade ≥ 4)	x	x	x	
Clinically significant bleeding attributed to grade 3 thrombocytopenia or requiring platelet transfusion	x	x	x	
Grade ≥ 3 oesophagitis onset during induction chemotherapy or within 2 weeks of starting radiotherapy	x	x	x	
Grade ≥ 3 pneumonitis onset within 3 months of starting radiotherapy	x	x	x	
Grade ≥ 3 elevation of ALT or AST lasting 8 days or more	x	x	x	
A concurrent elevation of ALT or AST $>3 \times$ ULN and total bilirubin $>2 \times$ ULN in whom there is no evidence of biliary obstruction or other causes that can reasonably explain the concurrent elevation	x	x	x	
Grade ≥ 3 nausea or vomiting not controlled by optimal outpatient anti-emetic treatment	x	x	x	
Grade ≥ 3 diarrhoea despite optimal outpatient anti-diarrhoeal medication use	x	x	x	
Other grade ≥ 3 effects thought to be directly treatment related to the combination of M6620 (Berzosertib) with radiotherapy or chemotherapy	x	x	x	
Any toxicity causing a delay of radiotherapy completion by greater than one week for Stage A	x	x	x	
Any toxicity causing radiotherapy delivery delay by ≥ 3 consecutive fractions for stage B	x	x	x	
Missing 2 consecutive doses of M6620 (Berzosertib) within a cycle due to Grade ≥ 3 toxicity	x	x	x	
Death due to drug related complications	x	x	x	
Cardiac toxicity: see section 9.1.2	x	x	x	
A delay of any of the 3 treatments of 7 days or more within a cycle due to treatment related toxicity	x	x	x	
AE/SAE defined as late DLT (onset 6 weeks after completion of radiotherapy) as per RTOG/EORTC late toxicity and Mellow Dysphagia score (Appendix C, D)				
Grade ≥ 3 lung and heart toxicity – onset 6 weeks after completion of radiotherapy	x	x	x	
Grade 3 oesophageal toxicity with an increase in Mellow score by ≥ 2 since baseline (need to exclude disease progression on CT and/or endoscopy and biopsy) - onset 6 weeks after completion of radiotherapy	x	x	x	

Grade 4 oesophageal toxicity - onset 6 weeks after completion of radiotherapy	X	X	X	
Medically important events in the context of this trial (considered dose limiting and possibly related to M6620 (Berzosertib) combined with Radiotherapy +/- chemotherapy by the TMG)		Email reporting form within 24 hours	Report in AE CRF	Non reportable
Any AE not listed above that is grade ≥ 3		X	X	
AE considered more severe than expected		X	X	
AE Grade <3 that is unexpected and thought to be directly treatment related to the combination of M6620 (Berzosertib) with radiotherapy +/- chemotherapy		X	X	
AE resulting in withdrawal		X	X	
Any late grade ≥ 3 toxicities – onset 6 weeks after completion of radiotherapy		X	X	
Any late grade 2 toxicities – onset 6 weeks after completion of radiotherapy			X	
Acute Hypersensitivity reaction		X	X	
Expected non-dose limiting toxicities		Email reporting form within 24 hours	Report in AE CRF	Non reportable
Anaemia		If grade ≥ 4	X	
Abdominal pain		If grade ≥ 4	X	
Cough			X	
Decreased appetite		If grade ≥ 4	X	
Elevated ALT/AST lasting less than 8 days		If grade ≥ 4	X	
Fatigue		If grade ≥ 4	X	
Headache			X	
Low lymphocytes			X	
Infusion-related site reaction		If grade ≥ 3	X	
Skin rash/discolouration related to sun exposure		If grade ≥ 4	X	
Grade <3 nausea or vomiting			X	
All other AEs, abnormal assessments or laboratory results		Email reporting form within 24 hours	Report in AE CRF	Non reportable
All other AEs, assessments, abnormal laboratory results, if clinically significant		If grade ≥ 3	X	
AE is life-threatening		X	X	
AE requires in-patient hospitalisation or prolongs existing inpatient hospitalisation		X	X	
AE results in persistent or significant incapacity or disability		X	X	
AE is a congenital anomaly or birth defect		X	X	
AE is any other medically important event		X	X	
Disease progression and resultant death		Email reporting form within 24 hours	Report in AE CRF	Non reportable
Hospitalisation (for progression or procedures planned prior to informed consent)				X

Clinical symptoms of progression				x
Death		Possibly related directly to M6620 (Berzosertib) or the combination of M6620 (Berzosertib) + radiotherapy +/- chemotherapy	Report death and reason on death notification CRF	

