3.2 Stage B

Primary Objective	Endpoints/ Outcome measures	Time point(s) for evaluation of end point
• To determine the best tolerated M6620 (Berzosertib) treatment schedule (or phase II recommended dose (RPTD)) administered concomitantly with radiotherapy (dCRT) in combination with cisplatin and capecitabine in the radical treatment of oesophageal cancer	Highest treatment schedule resulting in less than 45% dose limiting toxicity (DLT) rate (see section 9.1.2 for DLT definitions)	
 • Up to Week 24
Secondary Objectives	Endpoints/ Outcome Measures	
• To determine the safety and toxicity profile of M6620 (Berzosertib) administered concomitantly with dCRT in combination with cisplatin and capecitabine in the radical treatment of oesophageal cancer	
 • Any toxicity grade ≥ 3 graded according to CTCAE v4.03 and length of time for toxicity to resolve 	
 • Up to week 24
• To determine tolerance and ability to deliver M6620 (Berzosertib) in combination with standard dCRT	
 • Treatment tolerance and deliverability measured by proportion of patients completing at least 80% of the planned chemotherapy dose and at least 20 fractions of RT 	
 • End of induction chemotherapy and dCRT. End of week 11
• Efficacy and safety of the combination	
 • Objective tumour response (OR) as evaluated by CT scan and quantified by Response Criteria Evaluation (RECIST 1.1) and endoscopic and biopsy findings. • PFS and OS from D1 	
 • 24 weeks
Tertiary/Exploratory Objectives	Endpoints/ Outcome Measures	

 • To explore target effects in tissue 	
 • Change in level of ATR inhibition and apoptosis in M6620 (Berzosertib) treated tissue using IHC. • Genotyping of tumours • Aim to identify markers for oesophageal cancer in the blood 	
 • Biopsies at baseline, week 7 and 24 • Blood samples at baseline, week 7 and week 12
---	--	--

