9 TOXICITY MANAGEMENT

9.1 Dose Limiting Toxicity

9.1.1 Reporting a DLT

A dose limiting toxicity is a toxicity that is considered related to M6620 (Berzosertib) or the interaction between M6620 (Berzosertib) and radiotherapy or chemoradiotherapy. **Dose limiting toxicities should be reported within 24 hours of the site becoming aware using the SAE form and scan and email as a PDF attachment to [contact] and send an email notification to [contact].** For management of M6620 (Berzosertib) toxicities see section 9.3. Chemotherapy and radiotherapy toxicities should be managed as per standard practice.

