 - Any of the following (CTCAE criteria): Grade 2 or greater ventricular arrhythmia (second or third degree AV block), severe sustained/symptomatic sinus bradycardia less than 45 beats per minute (bpm) or sinus tachycardia >120 bpm not due to other causes (e.g., fever), persistent supraventricular arrhythmia (e.g., uncontrolled/new atrial fibrillation, flutter, atrioventricular nodal tachycardia, etc.) lasting more than 24 hours, ventricular tachycardia defined as >9 beats in a row or any length of torsades de pointes (polymorphic ventricular tachycardia with long QTc), or unexplained recurrent syncope
 - Symptoms suggestive of congestive heart failure with confirmed Ejection Fraction (EF) $<40\%$ (by 2D-echocardiogram or Multiple Gated Acquisition [MUGA] scan)
 - Troponin T: level which is consistent with myocardial infarction

Stage B

Acute DLTs will be defined as per NCI CTCAE v4.03 and include:

- Absolute neutrophil count (ANC) $<0.5 \times 10^9/L$ for >7 days
- Febrile neutropenia (fever of unknown origin without clinically or microbiologically documented infection) (ANC $<1.0 \times 10^9/L$, fever $\geq 38.5^\circ C$) lasting >3 days
- Infection (documented clinically or microbiologically) with Grade 3 or 4 neutropenia (absolute neutrophil count $<1.0 \times 10^9/L$)
- Platelets $<25 \times 10^9/L$
- Clinically significant bleeding attributed to grade 3 thrombocytopenia or requiring platelet transfusion
- Grade ≥ 3 oesophagitis onset during induction chemotherapy or within 2 weeks of starting radiotherapy
- Grade ≥ 3 pneumonitis onset within 3 months of starting radiotherapy
- Grade ≥ 3 nausea or vomiting not controlled by optimal outpatient anti-emetics
- Grade ≥ 3 diarrhoea despite optimal outpatient anti-diarrheal medication use
- Other grade 3 \geq effects thought to be directly treatment related to the combination of M6620 (Berzosertib) with chemotherapy or radiotherapy
- Any toxicity causing radiotherapy delivery delay by >3 consecutive fractions
- An elevation of ALT or AST $>5 \times ULN$ lasting 8 days or more
- A concurrent elevation of ALT or AST $>3 \times ULN$ and total bilirubin $>2 \times ULN$ in whom there is no evidence of biliary obstruction or other causes that can reasonably explain the concurrent elevation
- Missing 2 consecutive doses of M6620 (Berzosertib) within a cycle due to Grade ≥ 3 toxicity
- A delay of any of the 3 treatments of 7 days or more within a cycle due to treatment related toxicity

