9.3 Management of M6620 (Berzosertib) drug toxicities

No dose modifications of M6620 (Berzosertib) may be made (see 9.3.1 for exception in stage A2 below). Treatment may be interrupted because of a non-DLT of Grade 3 or higher, at the discretion of the Investigator. Treatment may be resumed when all toxicities have returned to grade 2 or less, at the discretion of the Investigator. If two consecutive doses of M6620 (Berzosertib) within a cycle are missed due to M6620 (Berzosertib) related Grade ≥ 3 toxicity, this constitutes a DLT, and no further M6620 (Berzosertib) will be administered. Missed doses due to \leq Grade 2 events, will be classified as non-compliance, not a DLT. A delay of any of the 3 treatments of 7 days or more within a cycle due to treatment related toxicity would be considered a DLT.

If the subject misses a dose of M6620 (Berzosertib) for any reason other than toxicity the dose should not be made up and the scheduling should continue as normal, from the next planned dose of M6620 (Berzosertib), unless it is a Tuesday dose which can be made up on the following day (Wednesday). If radiotherapy is withheld for toxicity or other reasons, M6620 (Berzosertib) should also be withheld and the dosing schedule should continue from the next planned dose once radiotherapy has resumed (see also section 8.4).

In Stage A2, if a patient experiences a DLT, they may continue on trial treatment at the next lowest dose level at the discretion of the treating investigator.

In Stage B, if a patient experiences a DLT, the TMG will convene to decide whether it is appropriate for the patient to continue receiving trial treatment, potentially at a reduced frequency of doses.

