12.8 Management of radiotherapy toxicity

Radiotherapy interruptions will usually not be necessary. However, if radiation is held for any reason, all systemic therapy must also be held, including M6620 (Berzosertib). Interruptions may be kept to a minimum by the use of ancillary therapy and vigorous nutritional support. Interruptions are permitted only on the basis of toxicity. However, if the RT interruptions are due to either technical reasons or due to bank holidays, the schedule should be made up to account for this either on a Saturday or at the end of the treatment.

Toxicity	Radiotherapy treatment interruption required:	Restart radiotherapy:
Oesophagitis	Grade 4; see management of symptoms below. Aim to limit interruption to 3 treatment days (fractions).	
Haematological toxicity		
Neutrophils	Stop RT treatment if neutrophils $<0.5 \times 10^9/L$ or	If levels recover to $0.5 \times 10^9/L$ (neutrophils) and $25 \times 10^9/L$ (platelets)
Platelets	platelet count $<25 \times 10^9/L$ and monitor every 48 hours. Note: systemic therapy should be interrupted initially as per local policy.	
Non-Haematological toxicity		
All toxicities	Grade 3: stop systemic treatment first and aggressive management should be pursued as per protocol, if no recovery to \leq grade 2 within 48h, consider withholding radiotherapy as follows:	
Vomiting	≥ 6 episodes of vomiting (\geq grade 3) lasting ≥ 3 days and unresponsive to antiemetics	Resolves to \leq grade 2
Diarrhoea	An increase from a patients usual bowel habit of ≥ 7 watery stools/day (\geq grade 3) and unresponsive to antidiarrhoeals	Resolves to \leq grade 2
Weight loss	Loss $\geq 10\%$ (\geq grade 2) of pre-treatment weight	
Other ¹	Grade 3: withhold radiotherapy and chemotherapy	Resolves to \leq grade 2

¹Rarely, non-treatment related or unexpected toxicities may require interruption of therapy at the discretion of the treating oncologist. Interruption of therapy may continue until the toxicity has regressed to \leq grade 2 to allow resumption of therapy; however, every effort should be made to limit treatment interruptions to 1-2 weeks

Oesophagitis

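### Stage B: a related toxicity that delays radiotherapy by exactly 3 consecutive fractions, and meets no other DLT criterion, is a DLT in the 14.5 table (≥3) but not in 9.1.2 (>3), the definition the primary endpoint cites

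*Protocol*

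**What the plan says.** Protocol 9.1.2 lists among the acute Stage B DLTs "Any toxicity causing radiotherapy delivery delay by >3 consecutive fractions". A separate item in the same list is "A delay of any of the 3 treatments of 7 days or more within a cycle due to treatment related toxicity".

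The table in Protocol 14.5 repeats the DLT list for site reporting. Its row for radiotherapy delay, ending "consecutive fractions for stage B", has ≥3 immediately before those words and is ticked as a DLT, for SAE reporting within 24 hours, and for the AE CRF.

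The Stage B primary endpoint in Protocol 3.2 points to one of these lists only: "see section 9.1.2 for DLT definitions". SAP 2.2 repeats the pointer. Neither document reconciles the two thresholds.

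Three other provisions matter. Protocol 9.1.1 limits DLTs to toxicities considered related to M6620 or to its interaction with radiotherapy or chemoradiotherapy. It also sets the timing: "Dose limiting toxicities should be reported within 24 hours of the site becoming aware using the SAE form". Protocol 9.3 gives the consequence for the patient: "In Stage B, if a patient experiences a DLT, the TMG will convene to decide whether it is appropriate" for that patient to continue trial treatment, possibly with fewer doses.

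**The concern.** A DLT is a yes/no outcome, and in Stage B it is the outcome on which the schedule is chosen. Two current lists in one protocol give different answers for a 3-fraction delay. That length is not far-fetched: for grade 4 oesophagitis, Protocol 12.8 aims to keep interruptions to 3 treatment days at most.

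The 14.5 table is what tells a site which events to send in as DLTs. A site that follows it would report an event that the endpoint's own definition leaves out. The first effect is on the patient, because the report brings the TMG together over whether trial treatment continues. The second is on the data. If nobody corrects the classification, the patient counts as a DLT in the by-schedule summary of Protocol 18.5 and, if the same coding is used there, in the dose-finding model.

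**Working it through.** The plan gives no figure to reproduce here. The check sets the two rules side by side and asks whether another Stage B criterion removes the difference.

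**1. Calendar.** Inputs: 25 daily fractions, Monday to Friday (Protocol 8.3.3), so chemoradiotherapy days 1-5, 8-12, 15-19, 22-26 and 29-33. Assume no Saturday make-up and no bank holiday. Delay = restart day minus first held day.

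- 3 fractions: a hold starting Monday or Tuesday restarts Thursday or Friday, 3 days later. A hold starting Wednesday, Thursday or Friday crosses the weekend and restarts 5 days later.
- 4 fractions: a Monday start restarts on Friday, 4 days later; any other start restarts 6 days later.
- 5 fractions: 7 days from any start.

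| Fractions held | Days to restart | 7-day rule | 9.1.2 (>3) | 14.5 (≥3) |
|---|---|---|---|---|
| 3 | 3 or 5 | no | **no** | **yes** |
| 4 | 4 or 6 | no | yes | yes |
| 5 | 7 | yes | yes | yes |

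At 2 fractions or fewer, neither fraction rule applies. The 7-day rule already covers radiotherapy delays of 5 fractions or more. The fraction rule therefore adds one delay length under 9.1.2 (4) and two under 14.5 (3 and 4).

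**2. Missed-dose rule.** Two consecutive M6620 doses missed within a cycle for grade ≥3 toxicity is a DLT on its own. Inputs are the dosing days in Protocol Table 8.3, with cycles taken as chemoradiotherapy days 1-21 and day 22 on. Take a 3-fraction hold starting at any of fractions 11 to 20 (radiotherapy weeks 3 and 4). The counts are starts, out of 10, at which the rule is met. All three hold timings are assumptions.

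| M6620 held | Schedule -1 | Schedule 1 | Schedule 2 |
|---|---|---|---|
| same days as radiotherapy | 0 | 1 | 1 |
| from 2 days earlier | 0 | 3 | 5 |
| from 2 days earlier to 2 days later | 1 | 5 | 9 |

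The rule closes part of the gap for grade ≥3 toxicity, but not all of it on any schedule.

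**3. Who is left.** The symbol decides DLT status only if all of these hold:

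- the delay is exactly 3 fractions;
- the toxicity is considered related under 9.1.1;
- no other 9.1.2 criterion is met, such as early oesophagitis, a grade ≥3 effect attributed to the combination, two consecutive missed doses, or a delay of 7 days or more to another treatment.

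**4. Size per patient.** Protocol 17.1 gives an expected minimum of 15 and a maximum of 25. One reclassified patient changes the crude whole-stage DLT percentage by 1/15 = 6.7 points or 1/25 = 4.0 points, against a 45% target.

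**The case against.** The strongest reply is that very little turns on this. Relatedness comes first: a hold put down to radiotherapy or chemotherapy alone is not a DLT under 9.1.1, whichever symbol is used. A grade ≥3 toxicity that does pass that test will often be a DLT already, through the criterion for other grade ≥3 effects of the combination. Any error runs in the cautious direction. The TMG meets on each Stage B DLT and may overrule the model (SAP 3.2), and the SRC can review DLTs (Protocol 19.2). These points stand and limit the scope. They do not remove the conflict, because no provision requires a reported DLT to be checked against 9.1.2.

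A reader might infer more than the documents support, in four ways.

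- *That every toxicity-caused 3-fraction delay is affected.* The relatedness condition and the overlapping criteria rule this out.
- *That a hold for grade 2 weight loss of 10% or more proves the case.* At grade 2 the grade ≥3 criteria fall away, and doses missed for such events "will be classified as non-compliance, not a DLT" under 9.3. But status would still depend on attribution. The weight-loss row in 12.8 also sits under a lead-in about grade 3 toxicity, so it is unclear whether grade 2 alone leads to a hold.
- *That the wrong coding will enter the TiTE-CRM.* SAP 7.3 describes a dedicated CRF for the model, but the documents do not show its threshold. SAP V2.0 leaves out the Stage B dose-allocation methods until a later update.
- *That 14.5 is shown to be a slip.* The endpoint's citation shows which definition governs, not which threshold the authors had in mind. The 12.8 aim of at most 3 treatment days is consistent with >3 but does not settle the matter.

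**Conclusion.** The inconsistency is real and lies in current text. For a related toxicity that meets no other criterion, a delay of exactly 3 consecutive fractions is a DLT in the reporting table and not in the definition that governs the primary endpoint. Confidence in that is high. If a site follows 14.5, the result is over-reporting and a TMG review that 9.1.2 would not call for; if it goes uncorrected, toxicity is over-counted.

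The calendar result assumes the planned weekday timetable. The missed-dose counts rest on assumed hold timings. The 6.7 and 4.0 points describe one hypothetical patient. The documents give no frequency for 3-fraction delays and no Stage B model specification, so neither the number affected nor any change in the recommended schedule can be estimated. This is a consistency correction worth making, not evidence that the Stage B design is unsound.

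**What to change.** In Protocol 14.5, change the Stage B radiotherapy-delay row from ≥3 to >3 consecutive fractions, and make the same change in any DLT form or CRF that copies it. Leave 9.1.2 and 12.8 as they are. Before Stage B opens, the sponsor should confirm that >3 is the intended threshold. If ≥3 was meant, 9.1.2 would have to change instead, and that would alter the endpoint definition.

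The cost is one symbol in the table and in the forms that repeat it. It needs no extra data and no change to treatment, and the endpoint is untouched if >3 is confirmed. SAP 1.2 already commits to an update with the Stage B methods before that stage recruits, so the DLT lists and forms can be aligned at the same time.
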